2.6 Adherence

In order to achieve adherence the script for telephone communications and visits plan is presented in the SOP report. In this way, researchers will be trained to: a) inform participants for the study and answer any question and b) ask from the participant to follow specific instructions regarding to sampling days.

The assessment for researcher's adherence will be examined through completion of the 'Tools List'. The participant's adherence includes the diary of meal intakes, where participants should note the time for all important activities, such as sleep/wake time, urine sample taken, working hours, etc.

2.7 Withdrawals

TEMP Study

Participants can withdraw from the study at any point without having to provide any explanation. Participants who discontinue completing the data collection prior to the end of the trial period will be withdrawn but their already collected data will remain available for analysis, unless they request otherwise. Reasons for withdrawal will be documented wherever possible.

2.8 Outcomes

The primary outcomes are the adipokines (leptin, adiponectin and ghrelin) and stress hormones (melatonin and cortisol) and their diurnal variations and circadian patterns in the two different climatological settings. The secondary outcome is the metabolic hormonal profiles of the participants.

2.9 Sample Size

To estimate the sample size, the sample size program by the MGH Biostatistics Center was used (Schoenfeld, 2010). We used the paired t test study design for calculating the power of this test, assuming that each subject has a pair of values (one for the urban setting and one for the rural mountainous setting). The variable used for the estimation of the sample size was one of the adipokines (serum leptin), since it is one the primary outcomes for the trial and there is no available information for urinary adipokines.

The input parameters were: significance level, within patient standard deviation, power and minimal detectable difference in means. Based on the literature, the within subject standard deviation of plasma leptin was assumed to be 3.53 ppb for females and 0.01 ppb for males (Saad et al., 1998), and we hypothesized a minimal detectable difference in leptin levels between the urban and rural mountainous settings to be atleast 1.9 ppb, based on other intervention studies (Hibi et al., 2017; Fontes-Villalba et al., 2016). Assuming a power of 80% and a two-sided 5% significance level, the sample size for this two-treatment crossover study was estimated to be 57 subjects.

3 Statistical Analysis

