2.1 General aspects

A 2 x 2 cross-over pilot study of healthy adults is proposed to prospectively describe the effect of ambient temperature gradient on diurnal hormonal secretion patterns. A total of 50-60 subjects will be followed for a period of 7 days firstly in an urban environment or in a village of the mountainous rural environment of Troodos and later, for the same period, in the alternate setting, during the summer period in Cyprus. The two settings will allow for the comparison of the circadian patterns of hormones secreted by the adipose tissue among different gradient temperature changes. Continuous quantification of skin temperatures on one day in each setting will allow for characterization of how skin temperature is affected by ambient temperature. Collection of all urine voids on one day in each setting will allow for quantification of the hormone secretion by the adipose tissue. In Table 1 the study characteristics of the non-pharmacological intervention are presented and in Figure 1 the order and duration of various procedures of the study are displayed.

Table 1. Study characteristics

Study Design	Randomised cross-over trial
Study groups	
Two study groups:
 
Group A: People initially staying in their permanent house in the urban area and then moving to the rural area for at least 7 days (Troodos Mountains – holiday house).
 
Group B: People initially staying in the rural mountainous area for at least 7 days (Troodos Mountains – holiday house) and then returning to their permanent house in the urban area.

Blinding	
The blinding of the participants to group assignment is not possible with the present study design. The blinding of the researchers to the subjects' identity is achieved by the coding of all study materials (urine containers, temperature sensors, questionnaires and diaries). The study personnel who will obtain the outcome measurements will be not informed of the group assignment. The personnel who will deliver the

intervention will not take any outcome measurements. All outcome assessors and data analysts will be kept masked to the allocation.

Randomisation Random allocation will be made in blocks in order to keep the sizes of treatment groups similar. Block randomisation with block size=30 and subjects no=60, will be performed using the function RAND() in Excel, that provides a random generated list, by an investigator with no clinical involvement in the trial

[figure not shown]

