3.2 Populations

Depending on the analysis, different characteristics for inclusion are defined in the population. For example:

In the Full Analysis, population is defined as:

- All subjects who were randomised.
- All subjects who completed both sampling days providing complete follow-up, independent of the duration of the sampling days.
- All subjects who completed both sampling days providing complete follow-up, independent of the stability of sleep/wake cycles and meal intakes.
- All subjects who completed both sampling days providing complete follow-up, independent of the number of received urine vials.

In the Final Analysis, population is defined as:

- All subjects who completed both sampling days providing complete follow-up, except those who dropped out.
- All subjects who adhere to the major criteria in the protocol (e.g. all subjects who stayed healthy or did not travel to another country within the study or completed both sampling days and completed the whole study duration).
- All subjects who did not substantially deviate with regards to sleep/wake cycles and meal intakes
- All subjects except those that have a health problem (diabetes and hypertension) and did not know by the beginning of the study.
- All subjects except those women that were pregnant and did not know by the beginning of the study.

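### The 57 subjects in SAP 2.9 are complete urban-rural pairs with no allowance for loss, so the stated 80% power is not delivered across the planned 50-60 subjects

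*SAP*

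**What the plan says.** SAP 2.9 uses a paired t test, "assuming that each subject has a pair of values (one for the urban setting and one for the rural mountainous setting"). It lists four inputs: significance level, within-patient SD, power and difference. The "standard deviation of plasma leptin was assumed to be 3.53 ppb for females and 0.01 ppb for males", and the section takes a "minimal detectable difference in leptin levels between the urban and rural mountainous settings to be atleast 1.9 ppb". The result is: "Assuming a power of 80% and a two-sided 5% significance level, the sample size for this two-treatment crossover study was estimated to be 57 subjects".

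Four other places bear on how many pairs will reach the analysis:

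- Section 2.1: "A total of 50-60 subjects will be followed for a period of 7 days" in one setting and later for the same period in the other. Table 1 in that section sets the randomisation list at 60.
- Section 2.7: "Participants can withdraw from the study at any point without having to provide any explanation". Data already collected stay available unless the participant asks otherwise.
- Section 3.2, Final Analysis: "All subjects who completed both sampling days providing complete follow-up, except those who dropped out". It also leaves out those who do not adhere to the major criteria (illness and foreign travel are examples), those who deviate substantially in sleep or meals, and those with previously unknown diabetes, hypertension or pregnancy.
- Section 3.2, Full Analysis: lists all randomised subjects, then three bullets that require both sampling days but disregard sampling-day duration, sleep and meal stability, and number of vials.

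No section gives an expected rate of loss or exclusion, and none says which population the 80% refers to.

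**The concern.** A paired calculation counts subjects who supply a usable value in both settings. If 57 such pairs are just enough, every participant lost or excluded has to be covered by enrolment above 57. The planned range starts below 57 and ends three above it, while the plan itself provides for withdrawal and prescribes several exclusions. A null leptin result would then be read against a printed 80% that the analysed set may not have.

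**Working it through.** **Inputs (SAP 2.9).** Two-sided alpha 0.05; target power 80%; difference 1.9 ppb; within-subject SD 3.53 ppb, the female value. The male value of 0.01 ppb plays no part in reproducing 57.

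**Formula.** SD of the difference = √2 × 3.53 = 4.99 ppb. For n pairs, the noncentrality is (1.9 / 4.99) × √n with n − 1 degrees of freedom. Power is the probability that the noncentral t exceeds the two-sided 5% critical value in absolute size.

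**Reproducing the plan's figure.** At n = 57 the noncentrality is 0.3806 × 7.550 = 2.873, the critical value is 2.003 and power is 80.6%. At n = 56 power is 79.9%. So 57 is the smallest n reaching 80%, and no inflation is hidden in it. Using n − 2 degrees of freedom, as in a two-sequence crossover analysis, changes the figures below by less than 0.1 point. Treating 3.53 as the SD of the difference gives 30, and the normal approximation gives 55; neither yields the printed number.

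**Power and detectable difference by number of pairs (same SD).**

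| Complete pairs | Power for 1.9 ppb | Difference detectable with 80% power |
|---|---|---|
| 60 | 82.6% | 1.84 ppb |
| 57 | 80.6% | 1.89 ppb |
| 56 | 79.9% | just above 1.90 ppb |
| 54 | 78.4% | 1.94 ppb |
| 50 | 75.1% | 2.02 ppb |
| 48 | 73.3% | 2.06 ppb |
| 45 | 70.4% | 2.13 ppb |
| 40 | 65.1% | 2.27 ppb |

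**Applied to the plan.**

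- 50 enrolled, nobody lost: 75.1%, which is 4.9 points below 80%. This needs no assumption about loss.
- 60 enrolled: 60 − 57 = 3 losses (3/60 = 5%) leave 57 pairs. A fourth leaves 56 and 79.9%.
- 10% loss (assumed): 60 × 0.9 = 54 pairs, 78.4%, short by 1.6 points; 50 × 0.9 = 45 pairs, 70.4%, short by 9.6 points.
- 20% loss (assumed, upper end of the range considered): 60 × 0.8 = 48 pairs, 73.3%; 50 × 0.8 = 40 pairs, 65.1%.

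**The case against.** **Two SDs are stated and only one is used here.** This is the strongest point. Section 2.3 does not restrict the trial to one sex. If the two stated variances are mixed by an assumed male share m, the within-subject SD is √((1 − m) × 3.53² + m × 0.01²). At m = 20% this is 3.16 ppb, and power is 79.7% at 45 pairs and 83.9% at 50. At m = 30% it is 2.95 ppb, and 40 pairs give 80.1%. On those inputs a modest share of men would absorb the loss. That stands as a condition: the power figures hold for an SD of 3.53 ppb. It does not rescue the 80% claim, because the printed 57 comes from 3.53 alone. Whether 0.01 ppb is a usable SD is a separate question.

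**The Full Analysis set may carry the comparison.** This is partly right. It would restore the sleep and meal deviators. It adds little for participants missing one setting: even if the mixed model in 3.9.3 uses their retained data, a single-setting record says little about a within-person contrast. The SAP does not name the set, which is part of the point.

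**Sixty may already contain an allowance.** Indeed 57/0.95 = 60, but the SAP does not label it so, and it gives 50 as an equally acceptable size. The 50-60 could also be read as subjects followed through both settings; even then, 50 falls short.

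**It is a pilot, reports 95% confidence intervals, and will use mixed models on several urine voids.** All true. This softens the consequence and means that the decimals should not be over-read. Section 2.9 nevertheless prints a formal power claim.

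**Stronger readings.** A reader might infer that the sample size is miscalculated, that the trial will be badly underpowered, or that more people must be enrolled. The SAP supports none of these. The 57 is correct for its inputs, the shortfall is small at 60 enrolled with modest loss, and 65% power needs 20% loss from the floor of 50.

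**Conclusion.** The concern holds in limited form. The 57 is a correct count of complete pairs with no loss allowance, and the enrolment range does not secure it. The firm part rests on the SAP's figures alone: the low end of the range gives 75.1% with perfect follow-up, and the high end tolerates three losses from all causes together. The remainder depends on a loss rate that the SAP does not state; at an assumed 10% the shortfall runs from about 2 points (60 enrolled) to about 10 (50 enrolled). Everything is conditional on the SD of 3.53 ppb and on the paired t test of 2.9, before any multiplicity correction. It is worth correcting because the correction is cheap, not because the trial is compromised.

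**What to change.** Do not enrol more; restate the claim.

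1. In 2.9, say that 57 is the number of participants with analysable leptin in both settings, and that no loss is included.
2. Name the population in 3.2 to which the power refers.
3. Replace the single 80% with power and detectable difference over the planned range, stating the SD used. For example, with SD 3.53 ppb: 50 pairs, 75%, 2.02 ppb; 54 pairs, 78%, 1.94 ppb; 57 pairs, 81%, 1.89 ppb; 60 pairs, 83%, 1.84 ppb. Label any loss rate as an assumption.
4. State that a null leptin result will be interpreted by its confidence interval and by the difference detectable at the achieved number of pairs.

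The cost is a few sentences in the SAP and a slightly less favourable stated power. No participant, procedure or analysis changes.

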3.3 Levels of confidence and p values

Statistical tests and confidence intervals will be two-sided. 95% confidence intervals will be presented wherever possible. The statistical significance level set will be at the 5% level.

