3.5 Multiple testing

Multiple testing will be accounted for, using the Benjamini-Hochberg (false discovery rate, FDR) method considering all the regression parameters of the primary and post-hoc analyses. Q-value <0.05 indicates statistical significance of an association after controlling the false discovery rate at 5%.

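### The 80% power in SAP 2.9 is stated before the false discovery correction of 3.5, holds at 57 complete pairs only if the female SD is applied to everyone, and sits beside an unexplained male SD of 0.01 ppb

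*SAP*

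**What the plan says.** - **SAP 2.9 (Sample Size)** sizes the trial on serum leptin with a paired t test, "assuming that each subject has a pair of values", one per setting. The within-subject SD is "assumed to be 3.53 ppb for females and 0.01 ppb for males". The target difference is 1.9 ppb, the power 80% and the level two-sided 5%. The conclusion is that "the sample size for this two-treatment crossover study was estimated to be 57 subjects". The section does not mention multiple testing.
- **SAP 2.1 (General aspects)** gives a range instead of one number: "A total of 50-60 subjects will be followed for a period of 7 days".
- **SAP 2.8 (Outcomes)** names five hormones as primary: leptin, adiponectin, ghrelin, melatonin and cortisol.
- **SAP 3.3** says: "The statistical significance level set will be at the 5% level".
- **SAP 3.5 (Multiple testing)** applies Benjamini-Hochberg, "considering all the regression parameters of the primary and post-hoc analyses", and takes q below 0.05 as significance once the false discovery rate is controlled. The number of parameters is not given.

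**The concern.** The sample size program takes one within-subject SD. Section 2.9 offers two that differ by a factor of 353, recruits both sexes, and reports one N. A reader cannot see what was entered without working backwards.

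The 80% also belongs to a single leptin test at an unadjusted 5%, which is not the rule by which 3.5 will call leptin significant. The 5% level in 3.3 does not settle this, because 3.5 says how significance is decided after correction.

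At stake is how a negative result is read. If leptin misses q<0.05, readers will weigh that against an 80% that applies before correction, at SD 3.53, with 57 complete pairs.

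**Working it through.** **Inputs from SAP 2.9:** difference d = 1.9 ppb; within-subject SD s = 3.53 (women) or 0.01 (men); two-sided 5%; power 80%. **From 2.1:** n = 50 to 60. **From 2.8:** five primary hormones.

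**Step 1: reproduce 57.** For a paired comparison the SD of the difference is √2 × s, and the t statistic has noncentrality d√n / (√2 × s) on n − 1 degrees of freedom. With s = 3.53 the SD of the difference is 4.99. At n = 57 the noncentrality is 1.9 × √57 / 4.99 = 2.87.

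| Complete pairs | Power, SD 3.53, unadjusted 5% |
|---|---|
| 50 | 75.1% |
| 56 | 79.9% |
| 57 | 80.6% |
| 60 | 82.6% |

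The smallest n that reaches 80% is 57, which is the plan's figure.

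**Step 2: try the other readings of the two SDs.**

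| SD used | Value (ppb) | n for 80% |
|---|---|---|
| Female SD for all | 3.53 | 57 |
| 75% women: √(0.75 × 3.53² + 0.25 × 0.01²) | 3.06 | 43 |
| 50:50 mix: √(0.5 × 3.53² + 0.5 × 0.01²) | 2.50 | 30 |
| Plain mean of the two SDs | 1.77 | 16 |

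Of these, only 3.53 for everyone gives 57.

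**Step 3: the male SD.** 3.53 / 0.01 = 353, and 1.9 / 0.01 = 190. The target difference would be 190 within-subject SDs in men, so a handful of men would be enough. The SAP cites a source for the value but does not comment on it.

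**Step 4: apply the rule of 3.5.** Benjamini-Hochberg rejects a hypothesis only if its p value is at most (k/m) × 0.05, where m is the family size and k the number of rejections. Since k ≤ m, this limit is never above 0.05, so the correction cannot raise power at a given SD. With m = 5, n = 57 and SD 3.53, the power of the leptin test at each fixed step is:

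| k | Level | Power |
|---|---|---|
| 1 | 0.01 | 58.4% |
| 2 | 0.02 | 68.3% |
| 3 | 0.03 | 74.0% |
| 4 | 0.04 | 77.8% |
| 5 | 0.05 | 80.6% |

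In practice k varies from trial to trial, so the procedure was simulated with independent t tests and 200,000 runs. The family sizes are assumptions, because the SAP gives none.

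| Family (n = 57, SD 3.53) | Real effects | Power for leptin |
|---|---|---|
| 5 tests | leptin only | 59% |
| 5 tests | three, equal size | 71% |
| 5 tests | all five, equal size | 78% |
| 5 tests | all five, others larger (noncentrality 4 against 2.87) | 80.4% |
| 15 tests | leptin only | 44% |
| 15 tests | all, equal size | about 78% |

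**Step 5: how far the answer depends on the SD.** At the 50:50 SD of 2.50 with leptin alone changing, power is 92% with five tests, 84% with fifteen, 81% with twenty, 79% with twenty-five and 78% with thirty.

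All of these are powers of the paired t test in 2.9, not of the mixed models in 3.9.3.

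**The case against.** The best defence is that 2.9 is open about its basis: one variable, a paired t test and a two-sided 5% level. It never claims 80% after false discovery control. Sizing on one outcome at the nominal level is common, and 2.1 calls the study a pilot. If 3.53 was applied to everyone, that is the cautious choice between the plan's two SDs. Power under a false discovery rule needs the number and size of the other real effects, which nobody has, and a family that includes post-hoc parameters is hard to count in advance.

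Much of this stands. The 57 is correct for its inputs, and nothing here calls for more participants. What remains is that the plan makes a formal power statement in one section and sets a different significance rule in another, without linking them.

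Two stronger readings are tempting and go too far:

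- **That power after correction must fall below 80% at SD 3.53.** It need not. If the other hormones change clearly more than leptin, leptin is tested at or near 5% and keeps about 80.4%.
- **That a sex mix makes the trial safe.** It does not do so in general. At SD 2.50 with leptin alone changing, power drops below 80% from about 25 tests, and 3.5 does not limit the family.

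**Conclusion.** The point holds as a correction to a stated figure. The 80% in 2.9 is the power of one leptin test before the correction of 3.5. It requires 57 complete pairs and the female SD for all participants, and at the lower end of the plan's own 50-60 range it is 75%.

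Under q<0.05 the power cannot be higher and is usually lower. For five independent tests at SD 3.53 and 57 pairs it lies between about 59% and 78% when the other effects are absent or equal to leptin's. Only the direction is certain. The size of the loss depends on the SD, the family size and the other effects, so no single corrected power can be quoted.

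A reader might also infer that 0.01 ppb is a mistake. The SAP does not show that: the value is unexplained and implausibly far from the female one, but only the cited source can settle it.

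**What to change.** 1. Restate the conclusion of 2.9, for example: *57 complete pairs give 80% power to detect a 1.9 ppb difference in serum/plasma leptin with a paired t test at two-sided 5%, before the false discovery correction of 3.5, applying the female within-subject SD (3.53 ppb) to all participants; power is 75% at 50 and 83% at 60 complete pairs.* The sponsor should confirm that 3.53 was in fact the value entered.
2. Add the power under q<0.05 for the primary family, stating the assumed number of tests and of real effects, and whether independence was assumed.
3. Check 0.01 ppb against its cited source, and correct or justify it.

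The cost is a change of SAP wording, one look at a cited source and one recalculation. Enrolment and design do not change. The downside is that the stated power becomes less favourable.

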3.1 Timing of Analysis

The final analysis will be performed after all urine samples and temperature data are collected from all participants and 'Data and Recruitment Form' is completed.

TEMP Study

Also, the final analysis will be performed on data transferred to the file 'Full Data'. This file will be the merge of the files 'Questionnaires', 'Urine Analysis Data' and 'Temperature Data':

- **Questionnaires:** answers from questionnaire A (baseline characteristics), Chronotype questionnaire and diaries.
- **Urine Analysis Data:** data on adipokines (ghrelin, adiponectin and leptin), cortisol, melatonin and other metabolites concentrations.
- **Temperature Data:** data on ambient air and skin temperature.

3.2 Populations

Depending on the analysis, different characteristics for inclusion are defined in the population. For example:

In the Full Analysis, population is defined as:

- All subjects who were randomised.
- All subjects who completed both sampling days providing complete follow-up, independent of the duration of the sampling days.
- All subjects who completed both sampling days providing complete follow-up, independent of the stability of sleep/wake cycles and meal intakes.
- All subjects who completed both sampling days providing complete follow-up, independent of the number of received urine vials.

In the Final Analysis, population is defined as:

- All subjects who completed both sampling days providing complete follow-up, except those who dropped out.
- All subjects who adhere to the major criteria in the protocol (e.g. all subjects who stayed healthy or did not travel to another country within the study or completed both sampling days and completed the whole study duration).
- All subjects who did not substantially deviate with regards to sleep/wake cycles and meal intakes
- All subjects except those that have a health problem (diabetes and hypertension) and did not know by the beginning of the study.
- All subjects except those women that were pregnant and did not know by the beginning of the study.

